8.4.3 Sensitivity Analyses

There are three planned sensitivity analyses that target the primary estimand. The first will be to relax the assumption that the baseline imputed $\text{PaO}_2/\text{FiO}_2$ is a confounding factor, so the analysis will be repeated but without stratification by the baseline imputed $\text{PaO}_2/\text{FiO}_2$ of ≤ 100 vs. > 100 . This analysis implies the baseline risk is the same across strata.

The second sensitivity analysis is based on a different administrative censoring rule and same analysis as the main analysis will be performed. Patients will be censored at the last ordinal scale assessment before or on the outcome visit if no recovery event is observed before or on the

outcome visit. This is to address the data collection limitation between the Day 30 outcome visit and Day 60 visit assessment related to the assessment of the primary endpoint.

The third sensitivity analysis is based on a different censoring rule for the prohibited immunosuppressive medications or immunotherapies and convalescent plasma treatment. In this sensitivity analysis, all data after the prohibited immunosuppressive medications or immunotherapies and convalescent plasma treatment will be excluded from the analysis. The time to recovery will be censored at the beginning of the prohibited immunosuppressive medications or immunotherapies or convalescent plasma treatment.

8.4.4 Supplementary Analyses

There are four planned supplementary analyses.

The first supplementary analysis changes the population level summary to the recovery rate ratio. The recovery rate ratio and the 95% CI will be estimated using a Cox proportional hazard model with treatment as the independent variable.

The second supplementary analysis changes the population level summary to the recovery rate ratio. The recovery rate ratio and the 95% CI will be estimated using a stratified Cox proportional hazard model with treatment as the independent variable and stratified by the baseline imputed $\text{PaO}_2/\text{FiO}_2$ of ≤ 100 vs. > 100 .

The third supplementary analysis changes the population to the safety analysis set and the same analysis as the main analysis will be performed except that treatment group will be based on actual treatment received.

The forth supplementary analysis changes the population to the efficacy analysis set including 26 subjects from baseline imputed $\text{PaO}_2/\text{FiO}_2$ of ≥ 201 stratification group and the same analysis as the main analysis will be performed.

8.5 Secondary Endpoint Analyses

8.5.1 Key Secondary Efficacy Analysis

All-cause mortality at Day 60 visit is the key secondary endpoint.

The primary estimand corresponding to the key secondary primary endpoint is defined as:

1. Treatment: 2.0 mg/kg (1.25 mL/kg) of Auxora administered at 0 hour and 1.6 mg/kg (1 mL/kg) administered at both 24 hours and 48 hours from the Start of the First Infusion of Auxora with local standard of care.
2. Population: Severe COVID-19 pneumonia patients with a baseline imputed $\text{PaO}_2/\text{FiO}_2 \leq 200$.
3. Variable: Dying by the Day 60 study follow-up visit.

4. Population level summary: difference in proportion of dying

Intercurrent events under consideration: 1) prohibited immunosuppressive medications or immunotherapies, 2) convalescent plasma treatment, and 3) treatment discontinuation.

The null and alternative hypotheses are:

- Null hypothesis H0: Proportion of dying by Days 60 is the same between the two treatment arms
- Alternative hypothesis H1: Proportion of dying by Days 60 is different between the two treatment arms

8.5.2 Main Analytical Approach

Proportion and 95% CI All-cause mortality at Day 60 visit will be displayed using a Clopper-Pearson interval and will be compared between the 2 treatment groups using a Cochran-Mantel-Haenszel test stratified by the baseline imputed $\text{PaO}_2/\text{FiO}_2$ of ≤ 100 vs. > 100 . Prohibited immunosuppressive medications or immunotherapies, convalescent plasma treatment and treatment discontinuation will be ignored (treatment policy strategy).

Patients with unknown death status at Day 60 visit will be treated as alive for the analysis if recovered during the study. Specifically, all patients who recovered, were discharged, and/or had 30 day follow up where they remained recovered, will be imputed at Day 60 as being alive/recovered if data is missing. Patients who discontinued from study before or on Day 1 and Day 60 survival follow up status as unknown are excluded from the primary analysis. This is not expected to introduce a bias in favor of either treatment arm since the clinical status is not likely to be affected within two days by the study treatment administered on Day 1.

To protect the trial level type 1 error rate at $\alpha = 5\%$ (two sided) between the two tests of the primary endpoint analysis and the key secondary endpoint analysis, the Benjamini and Hochberg testing strategy is used. Test statistics for Time to recovery and All-cause mortality at Day 60 are positive correlated and Hochberg testing strategy will protect the trial level type 1 alpha level.

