4 SAMPLE SIZE

In the initial design of Part 2 of the study, 320 patients in the baseline imputed $\text{PaO}_2/\text{FiO}_2 \leq 200$ subgroup and 80 patients in the baseline imputed $\text{PaO}_2/\text{FiO}_2 > 200$ subgroup were to have been randomized. A constant recovery rate ratio of 1.43 was assumed for patients receiving Auxora compared to Placebo in both subgroups. In order to provide power of approximate 90% to detect a difference in the recovery rate ratio of approximately 1.43 by a stratified 2-sided log-rank test at an overall 0.05 alpha level, given the 1:1 randomization, it was determined that the study would require 330 recovery events. With the study length of 30 days, the assessment of time to recovery required a sample size of 400 patients.

The enrollment of patients in the subgroup with a baseline imputed $\text{PaO}_2/\text{FiO}_2 > 200$ was stopped early because a blinded analysis of the data from the first 26 patients in the subgroup randomized into the study showed a low rate of mechanical ventilation or death. This finding was consistent with Part 1 of the study where no patients with a baseline imputed $\text{PaO}_2/\text{FiO}_2 > 200$ required mechanical ventilation or died.

The Part 2 study sample size was then reevaluated given that the primary endpoint would focus on the subgroup of patients with a baseline imputed $\text{PaO}_2/\text{FiO}_2 \leq 200$. A two group log-rank test with a 0.05 two-sided significance level would have 90% power to detect a difference in the recovery rate ratio of approximately 1.49 in the 320 patients with a baseline imputed $\text{PaO}_2/\text{FiO}_2 \leq 200$ who were randomized 1:1 to Auxora or Placebo.

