8.1.2 Significance Level and Confidence Interval

The statistical tests will be performed as two-sided with significance level of 5%. The confidence intervals will be determined with a confidence level of 95%.

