8.5.5 Supportive Secondary Efficacy Analysis

8.5.5.1 All-cause mortality at Day 30 visit

The analysis will be the same as the Day 60 visit analysis.

8.5.5.2 Proportion of patients requiring invasive mechanical ventilation or dying during the 60 days from the SFISD

Time to requiring invasive mechanical ventilation is defined as time from SFISD to the first time the patient requiring invasive mechanical ventilation or dying. Proportion of patients requiring invasive mechanical ventilation or dying is defined as the proportion at study Day 60. Day 60 rate for each treatment group will be estimated by the Kaplan-Meier procedure. Hypothesis testing will be based on the Kaplan-Meier estimates and standard errors estimated by Greenwood formula using the log-log transformation of the survival function stratified by the baseline imputed $\text{PaO}_2/\text{FiO}_2$ of ≤ 100 vs. >100 . Subjects who do not have death or require invasive mechanical ventilation in the record will be censored on the last known status date (administrative censoring). Patients who recovered, were discharged, had 30 day follow up where they remained recovered, and did not use invasive mechanical ventilation during the study, will be censored at Day 65 as being alive/recovered without event if data is missing.

8.5.5.3 Proportion of patients requiring invasive mechanical ventilation during the 60 days from the SFISD

The analysis will be the same as the proportion of patients requiring invasive mechanical ventilation or dying during the 60 days from the SFISD. Subjects who have death and do not require invasive mechanical ventilation will be censored on the date of death (hypothetical strategy). Patients who recovered, were discharged, had 30 day follow up where they remained recovered, and did not use invasive mechanical ventilation during the study, will be censored at Day 65 as being alive/recovered without event if data is missing.

8.5.5.4 Differences in Outcomes Measured by an 8-Point Ordinal Scale at Day 12

Proportion of patients in each category of 8-point ordinal scale at Day 12 will be calculated for each treatment group, and the odds ratio will be estimated. The proportion will be compared between the 2 treatment groups using a proportional odds model with fixed factor of treatment groups.

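### SAP 8.5.2 counts patients of unknown Day 60 status as alive on recovery alone, contradicts 8.5.5.2, and gives no value for never-recovered patients; the expected bias is small

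*SAP*

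**What the plan says.** SAP 8.5.2 compares Day 60 mortality by a CMH test stratified by baseline imputed PaO2/FiO2. Its general rule for missing vital status is "Patients with unknown death status at Day 60 visit will be treated as alive for the analysis if recovered during the study". The sentence that spells this out covers "all patients who recovered, were discharged, and/or had 30 day follow up where they remained recovered". The three conditions are joined by *and/or*, so any one of them is enough. Recovery is the primary endpoint event: at least 24 hours in category 6, 7 or 8 of the ordinal scale (SAP 8.4.1). It therefore includes discharge on oxygen and some inpatients.

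The only other rule in 8.5.2 excludes patients who discontinued on or before Day 1 and whose Day 60 status is unknown.

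SAP 8.5.5.2 (ventilation or death) and 8.5.5.3 (ventilation) word the matching rule cumulatively: "Patients who recovered, were discharged, had 30 day follow up where they remained recovered, and did not use invasive mechanical ventilation during the study". These patients are censored event-free at Day 65. In 8.5.5.2, all other patients without an event are censored at the last known status date, and 8.5.5.3 adopts the same analysis. SAP 8.5.5.1 makes Day 30 mortality follow the Day 60 analysis, so the looser rule carries over.

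SAP 8.5.3 adds a tipping-point analysis for missing deaths and a stratified Kaplan-Meier comparison. It gives neither the range of the first nor the censoring rule of the second.

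**The concern.** Three things are wrong with the rule as written.

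- It turns an unobserved outcome into certain survival, with no evidence after recovery or discharge.
- Whether a patient is set to alive depends on recovery, which the drug is meant to change. If one arm has more recoveries, more of its unknowns become survivors. The SAP argues absence of bias only for the Day 1 exclusions, not for this rule.
- It is incomplete. A patient who never recovered and left after Day 1 with unknown status needs a value, or an explicit exclusion, in a CMH test, and has neither. That choice could be made after the data are seen.

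Mortality shares the trial-level alpha with the primary test, so its main p-value should not rest on a rule that is partly undefined and at odds with a neighbouring endpoint.

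**Working it through.** **The passages applied to two patients**

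| Patient | SAP 8.5.2 | SAP 8.5.5.2 |
|---|---|---|
| Sent home on oxygen on Day 6, never reached again | Alive at Day 60 | No Day 30 follow-up, so censored at last known status |
| Never recovered, left after Day 1, status unknown | No value stated | Censored at last known status |

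**The plan's own figure.** The documents give no mortality rate, missingness rate or power for the Day 60 test, so that test has no stated figure to reproduce. The recovery design gives a scale. SAP Section 4 says "A constant recovery rate ratio of 1.43 was assumed for patients receiving Auxora compared to Placebo in both subgroups", with 90% power, "it was determined that the study would require 330 recovery events" and "the assessment of time to recovery required a sample size of 400 patients".

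- Schoenfeld: 4(1.960 + 1.282)² / (ln 1.43)² = 42.03 / 0.1279 = 329 events, against 330 stated. Freedman's formula gives 336. Power at 330 events is 90.1%.
- Implied recovered share: 330/400 = 82.5%.

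**Inputs for the size of the effect**

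- From the documents: 320 patients, so 160 per arm.
- Assumed: recovery of 88% on Auxora and 76% on placebo. This fits the design: the average is 82%, and ln(0.12)/ln(0.24) = 1.49, the planned ratio for 320 patients.
- Assumed: 5% or 10% unknown at Day 60, equally likely in recovered and non-recovered patients.
- Assumed: 5% to 15% of the recovered patients lost to follow-up have died.

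**Between-arm shift.** Patients set to alive = 160 × unknown share × recovered share.

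| Unknown | Per arm | Auxora | Placebo | Difference | Difference × 5–15% |
|---|---|---|---|---|---|
| 5% | 8 | 7.04 | 6.08 | 0.96 | 0.05–0.14 deaths |
| 10% | 16 | 14.08 | 12.16 | 1.92 | 0.10–0.29 deaths |

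Over both arms at 5% unknown, the hidden deaths are 13.12 × 5–15% = 0.7 to 2.0. Most of these cancel between arms, and only the difference biases the comparison.

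**More or unequal loss.** Hidden deaths per arm = 160 × 0.825 × unknown share × later death rate.

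- 5% unknown and 5% later death: 0.33. At 10% and 5%: 0.66. At 20% and 10%: 2.64.
- Unequal loss, 10% against 2%, with 5% later death: 0.66 − 0.13 = 0.53 deaths, or 0.33 percentage points.
- Unequal loss, 20% against 2%, with 10% later death: 2.64 − 0.26 = 2.38 deaths.

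**False-positive rate.** This was simulated with 40,000 runs per setting, 160 per arm, an unstratified test, true mortality of 15% in both arms, recovery of 84% against 76%, 2–10% unknown and 1–5% later death. The nominal rate in favour of Auxora is 2.5%.

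- Never-recovered unknowns excluded: 2.5–2.8%.
- Never-recovered unknowns counted as dead: 3.0–3.2% at 5% unknown, 3.9% at 10%.

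**Sensitivity to one death** (pooled two-proportion z-test, 160 per arm, assumed counts). 12 against 24 deaths gives p = 0.034, and 13 against 24 gives p = 0.054. One reclassified death can move a borderline result across 0.05.

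**The case against.** The strongest reply is that the rule hardly moves the comparison. With similar follow-up in both arms, the expected shift is roughly a tenth of a death at 5% unknown. The equal-missingness assumption is also doubtful: patients who never recovered have mostly died, and so are known, or are still in hospital with an inpatient Day 60 assessment (Protocol 8.11). Withdrawal means withdrawal of consent only, and patients with a new do-not-intubate order keep their mortality assessments (Protocol 6.2). This stands, and it limits the size of the point.

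A reader might infer that deaths after discharge are ignored. The documents do not support that. Ascertained deaths count, and contacts at Days 30 and 60 are planned for discharged patients. Only patients of unknown status are affected.

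Part of the difference from 8.5.5.2 is structural, since a time-to-event analysis can censor and a binary one cannot. The *and/or* also adds little, because discharge is category 7 or 8 and so already counts as recovery; the first sentence of the rule does most of the work. Neither argument explains why Day 30 evidence is needed for one endpoint and not the other, and neither supplies a value for never-recovered patients.

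The tipping-point analysis is aimed at missing deaths. It is a real safeguard, but it leaves the main p-value unchanged, and the SAP does not say whether patients already set to alive are varied.

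A reader might also conclude that the Kaplan-Meier analysis should replace the CMH test. Censoring at last contact would give discharged patients the later risk of everyone still under observation, including ventilated inpatients. That censoring is likely to be informative, so the replacement is not clearly better.

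**Conclusion.** The defect is real: single imputation to alive without later contact, a stricter rule for neighbouring endpoints, and no value for never-recovered patients lost after Day 1. It is worth correcting because the test is alpha-controlled.

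The expected bias is small: about 0.05 to 0.14 deaths between arms at 5% unknown and 0.10 to 0.29 at 10%. These figures rest on assumed recovery, missingness and later death rates, since the documents give no mortality or missingness rates.

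The stronger reading, that the quoted rule by itself materially inflates the chance of a false mortality benefit, is not supported. Clear inflation (3.0–3.9% against 2.5%) appears only when never-recovered unknowns are counted as dead, which the SAP does not say. Common or unequal loss to follow-up is the other route to a material effect.

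**What to change.** - In SAP 8.5.2, replace the *and/or* list with the cumulative condition of 8.5.5.2, and change the opening sentence of the rule to match, because that sentence alone makes recovery sufficient. Only patients with a Day 30 contact confirming recovery are then carried as alive at Day 60. State whether the final inpatient assessment that Protocol 8.11 substitutes for patients discharged on Days 25–29 counts as that contact.
- Keep the stratified CMH test as the main test.
- For all other patients of unknown status, recovered or not, use multiple imputation from baseline variables, treatment arm and last known ordinal status, under one rule for both arms.
- Apply the same imputation to Day 30 mortality, since 8.5.5.1 copies the Day 60 analysis.
- In 8.5.3, specify that the tipping-point analysis varies, by arm, the patients carried or imputed as alive, and give its range.
- Keep the Kaplan-Meier comparison as a sensitivity analysis with a stated censoring rule.

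The cost is SAP wording, some added analysis work and a slightly wider interval. Carrying patients who were recovered at Day 30 still depends on the primary outcome, but it rests on observed survival to about Day 30 and leaves only the remaining interval assumed.

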8.5.3 Sensitivity Analyses

There are three planned sensitivity analyses that both target the primary estimand. The first will be to relax the assumption that the baseline imputed $\text{PaO}_2/\text{FiO}_2$ is a confounding factor; the analysis will therefore be repeated but without stratification by the baseline imputed $\text{PaO}_2/\text{FiO}_2$ of ≤ 100 vs. > 100 . This analysis implies the baseline risk is the same across strata. The second sensitivity analysis is to examine the potential effects of missing death data due to dropout using tipping point sensitivity analysis. In the third analysis, day 60 death rate for each treatment group will be estimated by the Kaplan-Meier procedure. Hypothesis testing will be based on the Kaplan-Meier estimates and standard errors estimated by Greenwood formula using the log-log transformation of the survival function stratified by the baseline imputed $\text{PaO}_2/\text{FiO}_2$ of ≤ 100 vs. > 100 .

8.5.4 Supplementary Analyses

There are two planned supplementary analyses.

The first supplementary analysis changes the population to the safety analysis set. The analysis will be the same analysis as the main analysis except that treatment group will be based on actual treatment received.

The second supplementary analysis changes the population to the efficacy analysis set including 26 subjects from baseline imputed $\text{PaO}_2/\text{FiO}_2$ of ≥ 201 stratification group and the same analysis as the main analysis will be performed.

8.5.5 Supportive Secondary Efficacy Analysis

8.5.5.1 All-cause mortality at Day 30 visit

The analysis will be the same as the Day 60 visit analysis.

8.5.5.2 Proportion of patients requiring invasive mechanical ventilation or dying during the 60 days from the SFISD

Time to requiring invasive mechanical ventilation is defined as time from SFISD to the first time the patient requiring invasive mechanical ventilation or dying. Proportion of patients requiring invasive mechanical ventilation or dying is defined as the proportion at study Day 60. Day 60 rate for each treatment group will be estimated by the Kaplan-Meier procedure. Hypothesis testing will be based on the Kaplan-Meier estimates and standard errors estimated by Greenwood formula using the log-log transformation of the survival function stratified by the baseline imputed $\text{PaO}_2/\text{FiO}_2$ of ≤ 100 vs. >100 . Subjects who do not have death or require invasive mechanical ventilation in the record will be censored on the last known status date (administrative censoring). Patients who recovered, were discharged, had 30 day follow up where they remained recovered, and did not use invasive mechanical ventilation during the study, will be censored at Day 65 as being alive/recovered without event if data is missing.

8.5.5.3 Proportion of patients requiring invasive mechanical ventilation during the 60 days from the SFISD

The analysis will be the same as the proportion of patients requiring invasive mechanical ventilation or dying during the 60 days from the SFISD. Subjects who have death and do not require invasive mechanical ventilation will be censored on the date of death (hypothetical strategy). Patients who recovered, were discharged, had 30 day follow up where they remained recovered, and did not use invasive mechanical ventilation during the study, will be censored at Day 65 as being alive/recovered without event if data is missing.

8.5.5.4 Differences in Outcomes Measured by an 8-Point Ordinal Scale at Day 12

Proportion of patients in each category of 8-point ordinal scale at Day 12 will be calculated for each treatment group, and the odds ratio will be estimated. The proportion will be compared between the 2 treatment groups using a proportional odds model with fixed factor of treatment groups.

8-point ordinal scale will be imputed based on LOCF method based on the scale at discharge if the patient is discharged from hospital with the ordinal scale of 7 or 8 (composite strategy). 8-point ordinal scale will be imputed as 1 after the death (composite strategy).

8.5.5.5 Differences in Outcomes Measured by an 8-Point Ordinal Scale at Day 30

The analysis will be the same as the Day 12 analysis but extended at Day 30.

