8.4.2 Main Analytical Approach

Time to recovery through Day 60 visit will be displayed using a Kaplan-Meier estimate and will be compared between the 2 treatment groups using stratified log-rank test stratified by baseline imputed $\text{PaO}_2/\text{FiO}_2$ screening of ≤ 100 vs. > 100 . Prohibited immunosuppressive medications or immunotherapies, convalescent plasma treatment and treatment discontinuation will be ignored (treatment policy strategy). Death will be treated as not recovered and time to recovery will be censored at Day 65 (composite strategy). Patients, including withdrawal of consent patients, will be censored at the last ordinal scale assessment if no recovery event is observed during the study (administrative censoring). The trial level Type I error of 0.05 between the two tests of the primary endpoint analysis and the key secondary endpoint analysis is controlled using the Benjamini and Hochberg method.

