8.5.5.6 Number of Days in the Hospital

The date of each hospital admission and discharge will be collected for each patient. The number of days when patients are in hospital during the first 28 Days of the study will be summarized by treatment group and compared between the 2 treatment groups using an analysis of variance model, which includes treatment group in the model, which includes treatment group as the fixed effect in the model.

Two sets of analyses will be conducted. The first analysis is to assess patient benefit; the number of days in the hospital will be defined as 28 if the patient dies due to COVID-19 (composite strategy). The second analysis is to assess healthcare systems benefit; the number of days in the hospital before the patient's death will be used in the analysis (while alive strategy).

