8.6 Tertiary Endpoint Analysis

8.6.1 Change in Imputed PaO₂/FiO₂ Ratio

SpO₂ and FiO₂ will be examined at each scheduled time point. Worst value within the previous 24 hours at each scheduled time point will also be recorded. Conversion from SpO₂ to PaO₂ will follow [Table 3](#).

Table 3 Look up table for conversion SpO₂ to PaO₂

Measured SpO ₂ (%)	Imputed PaO ₂ (mmHg)
100*	167*§
99*	132*
98*	104*

97*	91*
96	82
95	76
94	71
93	67
92	64
91	61
90	59
89	57
88	55
87	53
86	51
85	50
84	49
83	47
82	46
81	45
80	44
79	43
78	42
77	42
76	41
75	40
74	39
73	39
72	38
71	37
70	37
69	37

* Generally considered unreliable on the basis of the sigmoidal shape of the hemoglobin-oxygen dissociation curve

§ Based on SpO₂ 99.5%.

Mean changes from baseline to each post-baseline visit and time point will be summarized by treatment groups for both at visit imputed PaO₂/FiO₂ value and worst value within the previous 24 hours of the visit imputed PaO₂/FiO₂ value.

Change from baseline over time in the imputed PaO₂/FiO₂ will be analyzed using a mixed effect model repeat measurement (MMRM) model with an unstructured covariance structure (if model is estimable). The analysis model will include Baseline value of the endpoint as a covariate, study day and treatment as fixed effect, study day by treatment as interaction, and subjects as random effect. Point estimates, 95% CIs and p-values for the difference between the Auxora treated patients and local standard care group at each scheduled time point will be obtained.

Similar analysis to the above analysis will be conducted for the change from baseline over time in the imputed PaO₂/FiO₂ endpoint using the last observation carried forward method as the missing value imputation method.

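### The Day-12/Day-30 ordinal models and the hospital- and ICU-day analyses leave out the PaO2/FiO2 stratum used in the SAP's main analyses; adding it is a cheap improvement, not the correction of an error

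*SAP*

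**What the plan says.** **Treatment-only analyses.** The Day-12 ordinal analysis (SAP 8.5.5.4) reads "The proportion will be compared between the 2 treatment groups using a proportional odds model with fixed factor of treatment groups". SAP 8.5.5.5 applies the same analysis at Day 30. Hospital days (SAP 8.5.5.6) are compared by an analysis of variance "which includes treatment group as the fixed effect in the model", in two forms: a composite that scores COVID-19 deaths as 28 days, and a while-alive count. Protocol 10.8.9 gives ICU days the same analysis as hospital days. SAP 8.5.5.7 has the same instruction but repeats the hospital heading, so that it covers ICU days is inferred from its place in the endpoint list.

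**Stratified analyses.** All use the ≤100 vs >100 cut of baseline imputed PaO2/FiO2:
- Recovery (SAP 8.4.2): "will be compared between the 2 treatment groups using stratified log-rank test stratified by baseline imputed" PaO2/FiO2.
- Day-60 mortality (SAP 8.5.2): "will be compared between the 2 treatment groups using a Cochran-Mantel-Haenszel test stratified by the baseline imputed" PaO2/FiO2. Day-30 mortality follows by reference.
- Ventilation or death (SAP 8.5.5.2), and ventilation alone by reference (8.5.5.3): "using the log-log transformation of the survival function stratified by the baseline imputed" PaO2/FiO2.

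**Status of the unstratified version.** For recovery and mortality (SAP 8.4.3 and 8.5.3) it is a sensitivity analysis, of which the SAP says: "This analysis implies the baseline risk is the same across strata". For the tertiary PaO2/FiO2 endpoint (SAP 8.6.1), "The analysis model will include Baseline value of the endpoint as a covariate".

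**The concern.** The SAP puts the severity stratum in its main analyses and keeps the unstratified test as a sensitivity check. For the ordinal and day-count endpoints the unadjusted fit is the only one specified, and no reason is given. The pattern suggests an incomplete update: Protocol 10.8.4 and 10.8.5 name no stratum for the ventilation endpoints and the SAP added one, but the neighbouring ordinal and day-count models stayed as they were.

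The stratum is plausibly prognostic. Enrolment above 200 was stopped because ventilation or death was rare there. That evidence concerns the 200 cut and does not measure the strength of a cut at 100.

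At stake is how sharply the supportive endpoints are estimated and tested. Protocol 10.8.2 gives them an inferential role alongside a descriptive one. The primary and key secondary conclusions do not depend on them.

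**Working it through.** **1. The plan's own figure.** The plan states no power, standard deviation or category mix for the ordinal or day-count endpoints. The nearest figure is the primary-endpoint event count. Schoenfeld: 4(1.960 + 1.282)² / (ln 1.43)² = 42.03 / 0.1279 ≈ 329 events, against 330 stated. That reproduces. From the plan I take N = 320, 1:1 allocation and two-sided 5%.

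**2. Assumed inputs.** Neither the share of patients at ≤100 nor the strength of the stratum is in the documents. Assumed: share 40% (25% as a check); stratum log-odds 0, 0.4, 0.7, 1.0; conditional treatment odds ratio (OR) 1.6; control-arm Day-12 distribution of 12, 12, 10, 10, 6, 2, 22, 26% over categories 1-8.

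**3. Ordinal model.** A proportional-odds model was fitted by maximum likelihood to the expected cell proportions, with and without the stratum, and standard errors (SE) were scaled to N = 320. Efficiency gain = (z adjusted / z unadjusted)² − 1. The last column comes from 3,000 simulated trials per setting (Monte Carlo SE 0.1-0.8 points).

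| Stratum log-odds | OR without / with stratum | SE(log OR) without / with | Gain, expected counts | Gain, simulation |
|---|---|---|---|---|
| 0 | 1.60 / 1.60 | 0.1996 / 0.1996 | 0% | 0.1% |
| 0.4 | 1.59 / 1.60 | 0.1996 / 0.1998 | 1.4% | 1.2% |
| 0.7 | 1.58 / 1.60 | 0.1995 / 0.2001 | 4.4% | 4.8% |
| 1.0 | 1.56 / 1.60 | 0.1994 / 0.2006 | 9.1% | 8.9% |

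Last row in full: with the stratum, ln 1.60 / 0.2006 = 0.470 / 0.2006 = 2.343. Without it, ln 1.564 / 0.1994 = 0.447 / 0.1994 = 2.244. (2.343 / 2.244)² = 1.09. Power is Φ(2.343 − 1.96) = 64.9% against Φ(2.244 − 1.96) = 61.2%. The gain is worth about 0.091 × 320 ≈ 29 patients.

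The SE does not fall when the stratum is added; it rises slightly. The whole gain comes from the OR, because an odds ratio is non-collapsible: leaving out a prognostic factor moves the estimate from a conditional OR to a marginal OR nearer 1.

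At 25% prevalence the simulated gains are 0, 1, 3 and 8%. The value at log-odds 1.0 is where the assumed grid stops. At a stratum OR of 4 (log-odds 1.39), other assumed category mixes with treatment OR 1.5 and shares of 30-50% give a loss of 12.4-15.6%. As a gain that is 1/(1 − 0.124) − 1 = 14% to 1/(1 − 0.156) − 1 = 18%.

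**4. Day-count ANOVA.** With share p at ≤100 and within-stratum standardized difference d, R² = p(1−p)d² / (1 + p(1−p)d²), and the gain from adding the stratum is R²/(1 − R²) = p(1−p)d². For p = 0.4: d = 0.4 gives 0.24 × 0.16 = 3.8%; d = 0.5 gives 0.24 × 0.25 = 6.0%.

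A simulation (6,000 trials per setting) assumed a lognormal stay with median 10 days and log-SD 0.75, capped at 28; 28-day death of 15% or 25%; median time to death of 13 or 8 days; and all deaths scored 28 in the composite. Gains:

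| Stratum log-odds | Composite | While-alive |
|---|---|---|
| 0 | −0.3% | −0.3% |
| 0.4 | 0.8% | 0.4-0.6% |
| 0.7 | 3.1-3.3% | 1.8-2.6% |
| 1.0 | 6.8-7.0% | 3.9-5.6% |

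Here the loss is precision in the usual sense: 7% efficiency is √1.07 = 1.034, a confidence interval about 3.4% wider. Estimated differences with and without adjustment agreed to within 0.01 day. These figures are not a ceiling either: at d = 0.8 and p = 0.2-0.5 the loss R² is 9-14%.

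**5. Validity.** Simulated type I error was 4.5-5.9% (ordinal) and 4.2-5.7% (days) with either model.

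**The case against.** The strongest reply is that this is a preference. The treatment-only models were already in Protocol 10.8.6 to 10.8.9 and the SAP follows them. No section commits to stratifying every efficacy analysis, and the first supplementary Cox model (SAP 8.4.4) is also treatment-only. A marginal odds ratio is a legitimate target. All of this stands, and it is why the point is an improvement and not a contradiction.

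Three stronger readings are tempting, and none is supported:
- **That the analysis ignores how patients were randomized.** The only stratification described (Protocol 3.1, SAP 3.1) concerns the ≤200 and >200 subgroups. The documents do not say that ≤100 vs >100 was a randomization stratum. Had it been, ignoring it would make the ANOVA conservative: at R² = 0.09, actual alpha is 2[1 − Φ(1.96/√0.91)] ≈ 0.040.
- **That adjustment would narrow the ordinal confidence interval.** On the log-OR scale it does not (0.1994 without, 0.2006 with). The benefit is power, and it comes with a change in what the OR means.
- **That 9% caps the loss.** It only marks the end of an assumed grid.

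What the reply leaves unanswered is why the SAP treats the unstratified analysis as secondary for recovery and mortality but as the sole analysis here, when the stratum is already derived.

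**Conclusion.** The point holds as a modest, low-cost improvement to supportive endpoints. The treatment-only tests are unbiased under randomization and keep their type I error, and the Benjamini-Hochberg pair is untouched.

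For hospital days the cost of omission is about 0-7% efficiency (composite) and 0-6% (while-alive), as a loss of precision. The ICU-day model shares the specification but was not simulated separately. For the ordinal models the cost is power through an OR drawn toward 1, equivalent to about 0-9% efficiency for stratum log-odds of 0 to 1.0, and about 14-18% at a stratum OR of 4.

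Every figure depends on assumed stratum share, prognostic strength, category mix and length-of-stay distribution. If the stratum is not prognostic, adjusting costs almost nothing (about 0.3% in the ANOVA). A reader might infer that the ordinal or day-count results would be wrong as planned; the documents and the calculations do not support that.

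**What to change.** Add the ≤100 vs >100 stratum as a fixed factor to the Day-12 and Day-30 proportional-odds models, to both hospital-day ANOVAs (composite and while-alive) and to the ICU-day model. State that the ordinal OR is conditional on the stratum. Keep the treatment-only fits as sensitivity analyses, as the SAP already does for recovery and mortality. Correct the heading of SAP 8.5.5.7 in the same edit so that it names ICU days.

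The Screening ordinal score may be added but is optional. With ventilated patients excluded and all patients on oxygen, it mainly separates high-flow from low-flow oxygen, and so overlaps with PaO2/FiO2, which is itself computed from FiO2.

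**Cost:** SAP wording and a few lines of code, with no new data. The ordinal OR becomes conditional instead of marginal, and the proportional-odds assumption then extends to the stratum. The ANOVA treatment difference keeps its meaning.
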